4.3.2 Infants

The following baseline characteristics of infants will be summarized and listed in the FASI, unless otherwise stated:

Characteristics at Birth

- Details of birth (vaginal delivery, vaginal delivery forceps/vacuum instrumental, cesarean – scheduled, cesarean – emergency)
- Gestational age (weeks)
- Sex (male, female)
- Weight (kg)
- Length (cm)
- Head circumference (cm)
- Apgar score 1 minute
- Apgar score 5 minute
- Apgar score 10 minute

Congenital anomalies

Characteristics at Screening

- Age (weeks)
- Sex (male, female)
- Weight-for-Age percentile categories
- Length/Height-for-Age percentile categories
- Head Circumference-for-Age percentile categories

Characteristics at Baseline

- Sex (male, female)
- Age (weeks)
- Exposure via breastmilk (months)

Medical History

Medical history of the infant will be summarized in the SAFI by System Organ Class (SOC) and preferred term (PT), following the same approach as previously described for medical history of the mother.

Vaccination Detail

Vaccination details of the infant will be listed in the SAFI.

4.4 PRIMARY ENDPOINTS ANALYSIS

4.4.1 Co-Primary Endpoints

The co-primary endpoints are:

- 1. Proportion of infants with B cell levels (CD19+ cells, absolute counts in blood) below the LLN, measured at Day 30 Visit after the mother's first ocrelizumab post-partum infusion
- 2. Estimated average oral daily infant dosage (ADID), calculated as the ocrelizumab average milk concentration over 60 days multiplied by an estimated infant milk intake of 150 mL/kg/day.

The estimand of the proportion of infants with B cell levels below the LLN is defined as:

 Population: All infants of women in the FASM population who have B cell levels measured at Day 30 Visit after the mother's first ocrelizumab post-partum infusion (FASI)

- Variable: Proportion of infants with B cell level (CD19+ cells, absolute counts in blood) below the age-adjusted LLN, measured at Day 30 Visit after the mother's first ocrelizumab post-partum infusion.
- Treatment: Commercial ocrelizumab of the mother (potential exposure via breastmilk).
- Handling of Intercurrent Events (ICEs):
 - 1. Incomplete dosing, including delayed second (300 mg) ocrelizumab infusion: all the B cell data will be included in the analysis.
 - 2. Infant did not receive any breastmilk before B cell measurement during the entire 30-day period after the mother's first ocrelizumab post-partum infusion: B cell data will be excluded from the analysis.
 - 3. Mother used other DMT during breastfeeding before B cell measurement on Day 30 Visit post ocrelizumab infusion 1: B cell data will be excluded from the analysis.
 - 4. Mother used other medication before B cell measurement on Day 30 Visit post ocrelizumab infusion 1 that is not allowed by protocol during breastfeeding: B cell data will be excluded from the analysis.
 - 5. Infant's blood sample collected before assessment window (i.e. before day 28, which is before *Analysis* Study Day 29): Data will be excluded from the analysis.
 - 6. Infant's blood sample collected after the assessment window: B cell data might be included or excluded depending on the cause of the delay and schedule of delayed visit:
 - i. Delayed due to operational reason and sample is collected more than 8 days after the assessment window (i.e. > Day 40, which is > Analysis Study Day 41): B cell data will be excluded.
 - ii. Delay due to illness of infant: sample collected between 32 days and 40 days while infant has an illness /or recovered from an illness (which is between *Analysis* Study Days 33 and 41): B cell data will be excluded on a case-by-case basis if the illness is likely to confound the B cell data.
 - 7. Infant's blood sample collected while infant has an illness: B cell data will be excluded on a case-by-case basis if the illness is likely to confound the B cell data.

B-cell reference ranges by week of life (absolute and percentage counts) are defined by Borriello et al. 2022 (Appendix 3). B cell data being confounded with illness will be determined by clinical team in a blinded manner before conducting the primary analysis.

 Population-level summary: The number and proportion of infants with B cell levels below LLN will be reported with the two-sided Clopper-Pearson 95% CI; no formal statistical testing will be done.

The estimand of the ADID in breastmilk is defined as:

- Population: All women in the FASM population who provide any breastmilk samples (PASM).
- Variable: Average oral daily infant dosage (ADID), calculated as the arithmetic mean of the mother's daily ocrelizumab milk concentration over 60 days post ocrelizumab infusion 1 multiplied by an estimated infant milk intake of 150 mL/kg/day. For example, arithmetic mean of the mother's daily ocrelizumab breastmilk concentration over 60 days (A)=20 ng/mL, assumed fixed daily milk intake (B) = 150 ml/kg, observed weight of infant at Day 30 visit (C) = 3kg. Average oral Daily Infant Dosage (ADID) = A x B x C=20 ng/mL x 150 mL/kg x 3kg=9,000 ng=0.009 mg=9 μg.
- Treatment: Commercial ocrelizumab.
- Handling of Intercurrent Events (ICEs):
 - 1. Incomplete dosing, including delayed second (300 mg) ocrelizumab infusion: all the ADID data will be collected and included in the analysis. No adjustments based on actual dose will be made.
 - 2. Mother used other DMT during breastfeeding: ADID data will be included.
 - 3. Mother used other medication not allowed by protocol during breastfeeding: ADID data will be included in the analysis.
 - 4. Mother has mastitis infection during the sample collection period: ADID data will be included from milk samples obtained from the non-infected breast (in case of bilateral mastitis, breastmilk sampling will be interrupted until the infection resolves).
- Population-level summary: Summary statistics together with two-sided 95% CI for the mean will be reported; no formal statistical testing will be done.

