### 4.5.3.2 Physical Examinations and Related Assessments

- Body weight (measured at every visit where a blood sample will be taken, i.e., at Day 30 [±2 days] post-infusion 1, and 1 month (+30 days) after the first or second dose of MMR vaccine or at Month 13 of age [+30 days] if MMR vaccine is not planned to be administered). Infant weight will be collected by a mobile nurse during home visits or by qualified site staff if the visit occurs at the site.
- Feeding schedule diary (during the treatment and sampling period): Women should record the number of breastmilk feeds and/or feed with formula milk (supplementation) on the day of the sample collection and the previous and following day, i.e., day of collection ±1 day. The mother's record of the feeding schedule diary will be collected by study personnel at the site or by a mobile nurse during visits to the mother.
- Feeding status (during the vaccination period): Women should record feeding status of the infant, i.e., whether exclusive breastfeeding, mixed feeding (partial breastfeeding along with infant formula and/or baby food), exclusive infant formula feeding, or fully weaned, at Months 2, 4, 6, 9, and 12, as applicable and depending on the infant's age at enrolment. The mother's record of feeding status will be collected by study personnel at the site or by a mobile nurse during visits to the mother.
- ASQ-3 at Months 2, 4, 6, 9, and 12, as applicable and depending on the infant's age at enrolment.
- Growth velocity (weight, length and head circumference), using growth charts according to the WHO Child Growth Standards (WHO 2022); as well as absolute values (other standard measurements recorded by e.g., the pediatrician as part of routine postnatal care may also be used) at Months 2, 4, 6, 9, and 12, as applicable and depending on the infant's age at enrolment.

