2.2 DETERMINATION OF SAMPLE SIZE

There is no formal sample size calculation, as no confirmatory hypothesis testing is planned. The primary analysis will be descriptive. The study will include at least 10 women with CIS or MS (in line with the locally approved indications) who are breastfeeding or planning to breastfeed.

With 10 infants, a precision (width of the two-sided 95% CI) of 0.443 is expected if one event is observed (defined as B cells below the lower limit of normal [LLN]) and a precision of 0.531 if two events are observed in the study. If no event is observed during the study, there is a 95% confidence that the event rate is below 0.31.

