4.4.4 Sensitivity Analysis for Primary Endpoint

For the primary endpoint of the proportion of infants with B cell levels below the LLN, measured at Day 30 after the mother's first ocrelizumab post-partum infusion, a sensitivity analyses will be performed including those samples collected outside the assessment window as well as those taken while infant has an illness.

4.4.5 Supplementary Analysis for Primary Endpoint

No supplementary analyses are planned for the estimation of proportion of infants with B cell levels below the LLN.

For the estimation of ADID in the breastmilk, the following supplementary analyses may be performed:

 ADID will only be calculated in cases where the complete dose of ocrelizumab was administered. Any subjects experiencing ICE 1 (incomplete dosing) will therefore be excluded from this supplementary analysis.

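### Early-weaned infants stay in the B-cell co-primary as exposed, no planned analysis isolates infants still breastfed near the Day 30 sample, and the late-sample rule has a gap after Day 40

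*SAP*

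**What the plan says.** **Breastmilk rule.** SAP 4.4.1, intercurrent event 2 of the B-cell estimand, excludes data when this applies: "Infant did not receive any breastmilk before B cell measurement during the entire 30-day period after the mother's first ocrelizumab post-partum infusion". Protocol 6.5.1 has the same rule. Neither sets a minimum duration or amount of feeding, or asks that the infant was still breastfed when the blood was drawn. The SAP describes the treatment attribute as potential exposure through milk.

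**Feeding information.** Entry requires willingness to breastfeed for at least 60 days, exclusively or with formula (Protocol 4.1.1). The feeding diary in Protocol 4.5.3.2 is completed "on the day of the sample collection and the previous and following day, i.e., day of collection" plus or minus one day.

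**Other B-cell analyses.**
- SAP 4.4.4 adds samples taken outside the window or during illness. It removes nobody.
- SAP 4.4.5 states: "No supplementary analyses are planned for the estimation of proportion of infants".
- SAP 4.4.6 has a type-of-feed subgroup with two levels, breast milk and partial breast milk with formula.
- SAP 4.5.1 and 4.6.4 summarise B cells whatever intercurrent events occurred.

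**Late samples.** Intercurrent event 6 opens by leaving inclusion dependent on the cause and timing of the delay, then gives two sub-rules. The first excludes data in this case: "Delayed due to operational reason and sample is collected more than 8 days after the assessment window", that is, after Day 40. The second covers illness: "sample collected between 32 days and 40 days while infant has an illness" or after recovery, with case-by-case exclusion. Intercurrent event 7 allows case-by-case exclusion of any sample taken while the infant is ill, with no day limit.

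**The concern.** The first co-primary asks whether infants exposed through milk show B-cell depletion. An infant breastfed on Day 1 and weaned on Day 2 counts in its denominator exactly like an infant fed throughout. If exposure has lapsed by the time of sampling, such infants pull the proportion towards what unexposed infants would show, which is the reassuring direction for a safety endpoint.

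The plan does not let the reader test this formally. No analysis restricts to infants still breastfed. The feed subgroup has no category for an infant no longer breastfed, and it does not say which diary day defines the type of feed. The protocol itself treats the amount of milk as relevant: Section 3.3.2 excludes non-singleton births partly because a different milk intake could confound the B-cell result, and Section 3.3 gives accounting for supplementation as the purpose of the diary.

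The late-sample gap is a separate matter of completeness. Protocol 6.5.1 promised that rules for samples beyond the window would be set in the SAP. The SAP sets a firm limit for one cause of delay and none for the other.

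**Working it through.** **1. The plan's own precision (SAP 2.2).** The plan states "With 10 infants, a precision (width of the two-sided 95% CI) of 0.443 is expected if one event is observed", "a precision of 0.531 if two events are observed in the study" and "If no event is observed during the study, there is a 95% confidence that the event rate is below 0.31". Exact two-sided 95% Clopper-Pearson limits give:
- 1/10: 0.0025 to 0.4450, width 0.4425 (stated 0.443)
- 2/10: 0.0252 to 0.5561, width 0.5309 (stated 0.531)
- 0/10: upper limit 1 − 0.025^(1/10) = 0.3085 (stated 0.31)

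All three reproduce.

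**2. Days the diary covers.** For 1×600 mg the milk sampling days are 0, 1, 7, 30 and 60. With one day either side, nothing is recorded from Day 9 to Day 28, which is 20 days. For 2×300 mg the extra samples on Days 14, 15 and 21 add diary Days 13–16 and 20–22, so the long gap applies only to 1×600 mg mothers. In both regimens Days 6–8 and 29–31 are covered.

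**3. Dilution.** Inputs: background rate 2.5%, because the lower limit of normal is the 2.5th percentile (SAP Appendix 3); n = 10; k infants with lapsed exposure and true rate p in exposed infants, both assumed. The expected proportion is [(10 − k)p + k × 0.025]/10. For p = 0.30:
- k = 1: (9 × 0.30 + 0.025)/10 = 0.2725
- k = 2: (8 × 0.30 + 0.050)/10 = 0.245

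Over p from 0.10 to 0.50, the relative fall is 7.5–9.5% for k = 1 and 15–19% for k = 2.

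**4. A zero-event result.** The upper limit for 0/n is 1 − 0.025^(1/n): 30.8% for n = 10, 33.6% for n = 9 and 36.9% for n = 8. If one or two of ten infants were no longer exposed, the last two figures describe what the exposed infants support.

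**5. How many might be weaned.** The documents give no figure for this population. Protocol 3.3.2 cites survey figures of 58.3% breastfed at 6 months and 35.3% at 1 year. The implied monthly stopping rate is 1 − (35.3/58.3)^(1/6) = 8.0%, or about 0.8 of 10 infants in a month. Applying it here is an assumption: the infants are 2–24 weeks old at dosing and their mothers intend to feed for 60 days.

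**6. Late samples, by cause.**

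| Situation | Up to Day 40 | After Day 40 |
|---|---|---|
| Operational delay | no exclusion stated | excluded |
| Illness delay, ill at sampling | case by case | case by case (event 7) |
| Illness delay, recovered | case by case | no specific rule |

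The case-by-case test asks whether the illness confounds the count. It does not ask whether the sample still represents Day 30.

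**The case against.** The breastmilk rule can be read as a deliberate estimand: treatment is potential exposure, mixed feeding is eligible, and protocol and SAP agree. An infant weaned partway through was exposed for some time, so treating that infant as carrying only the background rate is the worst case. With 0 to 1 infant affected, a shift from 30% to about 27% is small beside a planned interval 0.443 wide. Weaning would often be visible too: the diary covers Days 29–31, Protocol 3.1.3 asks for the Day 30 milk sample on the day of the infant's blood draw, and SAP 4.6.5 summarises feeds by study day with a listing. Any replacement threshold is itself arbitrary.

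Most of this stands. It is a reason to leave the primary rule alone and to keep the size modest. It does not supply the missing analysis: readers would have to combine two listings themselves, with no prespecified result in infants still breastfed.

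A reader might also infer that illness-delayed samples after Day 40 are counted as Day 30 results and dilute depletion. The documents do not support that. The opening of intercurrent event 6 leaves inclusion open, and event 7 still applies if the infant is ill at sampling. Lateness alone does not remove exposure: Protocol 3.3 expects milk excretion to be highest over the first 60 days, an infant still breastfed at Day 50 has had more cumulative exposure than at Day 30, and the limit of normal is set by week of life. The direction of any bias is not established.

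**Conclusion.** The breastmilk point holds and should be corrected. An infant weaned soon after the infusion counts fully in a co-primary safety proportion, and no planned B-cell analysis isolates infants still breastfed near the sample. The effect is probably small: with one of 10 infants affected, an assumed true rate of 30% would be expected to show as about 27.3%, and the zero-event limit of 30.8% would correspond to 33.6% in nine exposed infants. These figures assume that exposure has lapsed by sampling and that weaned infants carry the 2.5% background. The number weaned is not in the documents. The bias, where present, runs towards reassurance.

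On late samples the finding is narrower: there is no stated rule for an infant who has recovered from illness and is sampled after Day 40, which sits oddly beside the firm Day 40 limit for operational delay. This is a gap in the rules, not a demonstrated bias.

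**What to change.** Leave intercurrent event 2 unchanged, and then:
- In SAP 4.4.5, add one supplementary analysis of the proportion below the lower limit of normal, restricted to infants with breastmilk feeds recorded in both the Day 7 and the Day 30 diary entries. State in advance how a missing entry is treated.
- In the B-cell listing of SAP 4.4.2, show feeding status beside each infant's result.
- In intercurrent event 6, apply the same Day 40 analysis limit whatever the cause of delay. Samples beyond it remain in the SAP 4.4.4 sensitivity analysis.

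The data are already collected, so the cost is SAP wording, one table line and a listing column. The supplementary interval will be slightly wider with one or two fewer infants. Two diary points also cannot prove continuous feeding between them, least of all for 1×600 mg mothers, so the result should be presented as support for the primary analysis and not as its replacement.

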4.4.2 Analytical Approach for Co-Primary Endpoints

The number and proportion of infants with B cell levels below the LLN at Day 30 after the mother's first ocrelizumab post-partum infusion will be presented in the FASI, including Clopper Pearson 95% CI. A corresponding listing will be presented for B cell levels (absolute count) at Day 30, including whether any ICEs led to exclusion of subject's data from the analysis.

Summary statistics for the ADID will be presented in the PASM, including 95% CIs for the mean based on the t-distribution. Average oral daily infant dosage will be calculated

over all days for which measurements are available, assuming any missing assessments are missing at random. Breastmilk ocrelizumab concentrations below the limit of quantification (BLQ) will be imputed to zero for the calculation of summary statistics. A corresponding listing will be presented, including whether any ICEs led to exclusion of subject's data from the analysis.

4.4.3 Handling of Missing Data

No data will be imputed unless otherwise stated. Every effort will be made to ensure all samples with all supporting information are collected for B cell measurement.

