4.5 SECONDARY ENDPOINTS ANALYSES

4.5.1 B Cell Levels in Infants

B cell levels (CD19+ cells, absolute counts and percentage of lymphocytes) in infants at Day 30 after the mother's first ocrelizumab post-partum infusion will be summarized descriptively in the FASI, irrespective of the occurrence of any ICEs identified for the primary endpoint.

4.5.2 Parameters to Evaluate the Transfer of Ocrelizumab into Breastmilk

The area under the milk concentration-time curve (AUC) of ocrelizumab in mature breastmilk (i.e., milk produced after Day 14 post-partum) over 60 days after the first post-partum ocrelizumab infusion will be calculated using the following time points depending on the dosing schedule:

- If receiving 1x600 mg: before infusion and at 24 hours (Day 1), 7 days, 30 days and 60 days post-infusion
- If receiving 2x300 mg: before infusion 1 and at 24 hours (Day 1), 7 days, 14 days, 15 days (24 hours after infusion 2), 21 days, 30 days and 60 days post-infusion 1

Summary statistics will be presented in the PASM for the following PK parameters of ocrelizumab in the breastmilk measured over 60 days after the mother's first postpartum ocrelizumab infusion, irrespective of the occurrence of any ICEs identified for the primary endpoint:

- Area under the milk concentration-time curve of ocrelizumab in mature breastmilk (AUC)
- Average ocrelizumab milk concentration (C_{mean})
- Peak ocrelizumab milk concentration (C_{max})
- Time to reach peak milk concentration (t_{max}, days)

Summary statistics for each parameter will be presented in the PASM, irrespective of the occurrence of any ICEs identified for the primary endpoint. A corresponding listing will be produced.

For summary stats of all PK parameters other than AUC, concentrations reported as BLQ are set to zero. For AUC calculation, BLQ values before the first measurable concentration are set to zero, and to missing after the last measurable concentration.

Other PK and exposure parameters may be calculated and summarized as appropriate, based on the data obtained.

Subject-level plots of the concentration of ocrelizumab in breastmilk over time will be produced in the PASM.

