4.5.3 Relative Infant Dosage (RID) and Maximum Oral Daily Infant Dosage (MDID)

The estimated maximum oral daily infant dosage (MDID) will be calculated at the subject level as the peak ocrelizumab milk concentration measured over 60 days after the mother's first post-partum ocrelizumab infusion multiplied by an estimated infant milk intake of 150 mL/kg/day.

The average relative infant dose (RID, %) over 60 days will be calculated as the ADID (μ g) divided by the average maternal dosage (μ g) over 60 days multiplied by 100.

i.e.,

Average Oral Daily Infant Dosage (ADID) (A) = $9 \mu g$

Average maternal dosage over 60 days (B) = total dose / 60 = 600 mg / 60 = 10 mg = 10,000 μ g

Average RID (%) based on ADID = $(A / B) \times 100 = (9 / 10,000) \times 100 = 0.09\%$

The maximum RID (%) will also be calculated, where MDID is substituted for ADID in the formula above, i.e.

Maximum RID (%) = (MDID / Average maternal dosage over 60 days) x 100

Breastmilk ocrelizumab concentrations reported as BLQ will be imputed to zero for the calculation of summary statistics.

Summary statistics for MDID, average RID and maximum RID will be presented in the PASM, irrespective of the occurrence of any ICEs identified for the primary endpoint.

The analysis will be repeated for the following subgroups:

• The first dose of ocrelizumab post-partum (1x600mg, 2x300mg)

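### The co-primary ADID is computed as an unweighted mean of four or seven unevenly spaced milk samples, which is not the 60-day average concentration that defines the endpoint

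*SAP*

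**What the plan says.** Protocol Section 2 (Table 1) and SAP 4.4.1 (list of co-primary endpoints) build the ADID on the average milk concentration over 60 days. Protocol 3.3 explains it as the average amount available to the infant over that period.

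The estimand variable in SAP 4.4.1 turns this into the arithmetic mean of the mother's "daily ocrelizumab milk concentration over 60 days post ocrelizumab infusion 1", and SAP 4.4.2 takes the mean "over all days for which measurements are available, assuming any missing assessments are missing at random". The result is summarised "including 95% CIs for the mean based on the t-distribution".

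SAP 4.5.2 gives the sampling days:
- "If receiving 1x600 mg: before infusion and at 24 hours (Day 1), 7 days, 30 days and 60 days post-infusion"
- for 2x300 mg, "before infusion 1 and at 24 hours (Day 1), 7 days, 14 days, 15 days (24 hours after infusion 2), 21 days", then Days 30 and 60.

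A 60-day AUC is planned in 4.5.2 as a separate secondary parameter, with no named integration rule. Its handling of values below the limit of quantification (BLQ) is: "For AUC calculation, BLQ values before the first measurable concentration are set to zero, and to missing after the last measurable concentration". ADID does not use it. The only supplementary ADID analysis, in SAP 4.4.5, is optional and concerns dosing: "ADID will only be calculated in cases where the complete dose of ocrelizumab was administered". SAP 4.5.3 derives the average relative infant dose (RID) from ADID and, for first dose 1x600 or 2x300, states: "The analysis will be repeated for the following subgroups". SAP Section 5 lists one change from the protocol, the name of an analysis set.

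**The concern.** There is no daily series to average. Taken literally, an arithmetic mean over the days with measurements gives a Day 1 sample the same weight as a Day 30 sample, although the latter stands for a far longer stretch of the 60 days. The two regimens have different sampling calendars, so their averages weight time differently and are then pooled into one mean and one t-interval.

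The available-days rule adds a second problem. Each sample sits at a fixed place on a changing curve, so losing one shifts that woman's mean even if the loss is completely unrelated to her concentrations. Assuming missing at random does not repair this. Protocol 6.5.1 left sensitivity analyses based on alternative imputation to the SAP, and the SAP gives none for ADID.

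At stake is the accuracy of a co-primary exposure estimate and of the average RID. The error is set by the sampling calendar and does not shrink as women are added.

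**Working it through.** **The plan's own figure.** SAP 4.4.1 gives ADID = A x B x C = 20 ng/mL x 150 mL/kg x 3 kg = 9,000 ng = 9 μg, and SAP 4.5.3 gives RID = 9/10,000 x 100 = 0.09%. Both reproduce. Only A, the 60-day average concentration, is at issue. ADID and average RID are proportional to A, so a percentage error in A passes straight through.

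**Weights, with no assumption about the milk profile.** By the linear trapezoidal rule a sample's weight is half the distance between its neighbours, divided by 60.
- 1x600: Day 1, (7-0)/2/60 = 5.8%; Day 7, (30-1)/2/60 = 24.2%; Day 30, (60-7)/2/60 = 44.2%; Day 60, 15/60 = 25.0%; pre-dose 0.8%. The SAP rule gives each post-dose sample 25%. Days 1 and 7 together: 50% against 30%.
- 2x300: Days 1, 7, 14, 15, 21, 30, 60 have weights 5.8, 10.8, 6.7, 5.8, 12.5, 32.5, 25.0%. The SAP rule gives each 1/7 = 14.3%. Samples to Day 21: 5/7 = 71% against 42%.

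**Size, under a stated assumption.** The documents give serum half-lives of 26 days (average, Protocol 3.3) and 53 days (longest recorded, in one woman, Protocol 3.3.2). They give no milk profile. I assume that milk declines with these half-lives and rises with an uptake half-life u of 0.25 to 2 days: C(t) = exp(-t ln2/h) - exp(-t ln2/u). For 2x300, half of C(t) plus half of C(t-14), with the Day 14 sample taken before infusion 2. Truth is the integral over 0-60 days divided by 60; the pre-dose value is 0.

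One case in full (1x600, h = 26, u = 0.25). Concentrations on Days 1, 7, 30, 60 are 0.911, 0.830, 0.449, 0.202.
- True average: 0.493.
- SAP mean: 2.392/4 = 0.598, which is +21%.
- Trapezoid: (0.46 + 5.22 + 14.71 + 9.77)/60 = 0.503, which is +2%.
- Day 60 missing: SAP mean 2.190/3 = 0.730, which is +48%.

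All complete-data errors:

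| h (days) | u (days) | 1x600 SAP mean | 1x600 AUC/60 | 2x300 SAP mean | 2x300 AUC/60 |
|---|---|---|---|---|---|
| 26 | 0.25 | +21.3% | +2.0% | +7.8% | +1.0% |
| 26 | 1 | +2.5% | +0.1% | -2.1% | -0.8% |
| 26 | 2 | -8.0% | -1.6% | -6.5% | -0.5% |
| 53 | 0.25 | +8.0% | 0.0% | -2.5% | -0.3% |
| 53 | 1 | -5.7% | -1.4% | -10.0% | -1.7% |
| 53 | 2 | -13.3% | -2.6% | -13.6% | -1.5% |

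**Day 60 missing, h = 26.** The SAP mean is off by +8% to +48% (1x600) and -1% to +17% (2x300). An AUC cut at Day 30 but still divided by 60 is worse: -31% to -38% and -42% to -48%.

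**Interval coverage.** Ten women; between-woman CV 37% (from the four-woman rituximab range in Protocol 1.3: ln(0.097/0.046)/2.059 = 0.362 on the log scale); assumed 20% CV per sample. With half-life varying by an assumed 30% CV around 26 days and uptake spread over 0.25 to 2 days, coverage of the true mean is about 95% for the SAP mean against 93 to 94% for AUC/60 (1x600), and 93 to 94% against 93% (2x300). The SAP mean's bias is then about +8% and +1%, against an interval half-width of about 28 to 31%. Around a 53-day median, coverage is 92% against 93% (1x600) and 84% against 92% (2x300).

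**The case against.** The strongest defence is that little may turn on this. The error can be close to zero (+2.5% and -2.1% at 26 days with one-day uptake). Its direction is unknown, there is no test and no ADID threshold, and SAP 4.4.6 plans no regimen subgroups for ADID. A 60-day AUC, listings and individual plots are already planned. All of that stands, and it limits the consequence. It does not make the mean of the sampled days an average over 60 days. AUC/60 was closer to the truth in all 12 complete-data cases above, and average RID is summarised by regimen.

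Three stronger inferences are tempting but unsupported:
- *ADID will be overstated.* An early peak pushes the mean up and a slower rise pushes it down; the documents do not settle which applies.
- *The 95% interval is invalid.* With women differing in half-life and uptake around 26 days, coverage is hardly changed. It falls materially only if women share similar profiles (as low as 82% on 1x600 if all ten had identical 26-day curves) or if half-lives are long.
- *A pre-dose zero will be averaged in.* That would multiply ADID by 4/5 or 7/8, but the SAP's reference to the period after infusion 1 points to post-dose samples only. The SAP should simply say so.

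**Conclusion.** The point holds. The averaging rule in SAP 4.4.1 and 4.4.2 does not estimate the 60-day average concentration that defines the co-primary endpoint, and it weights time differently on the two regimens. The weight comparison (50% against 30%; 71% against 42%) needs no assumption about the milk profile. The percentage errors do: at a 26-day half-life with uptake of 0.25 to 2 days, -8% to +21% on 1x600 and -7% to +8% on 2x300, against about 2% at most for AUC/60; at 53 days, -13% to +8% and -14% to -2%. A missing Day 60 sample can add considerably more.

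The consequence is a calendar-dependent bias in a descriptive exposure estimate and in the average RID. No test decision is affected, nor are the planned AUC or the maximum daily dosage. The correction is cheap and worth making.

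**What to change.** 1. In SAP 4.4.1 and 4.4.2, define A as AUC(0-60)/60 by the linear trapezoidal rule on actual sampling times. Use the pre-dose sample only as the time-zero point and set BLQ values to zero. State how a last sample inside the ±2-day window is brought to Day 60; reading it by a straight line keeps total error between -1.9% and +2.3% at 26 days.
2. Leave the rest of the ADID formula unchanged, including 150 mL/kg/day and the infant-weight factor, so that RID in 4.5.3 stays consistent. Whether ADID should be per kg or absolute is a separate question: dropping the weight here would turn 9 μg into 3 μg/kg.
3. Do not impute in the main analysis, in line with Protocol 6.5.1. A woman without a usable Day 60 sample has no AUC-based ADID and is listed with the reason. Do not divide an AUC ending at Day 30 by 60. Any extrapolation to Day 60 is a sensitivity analysis only.
4. Keep the arithmetic mean of post-dose samples, in all women with any milk sample, as a sensitivity analysis. Reconcile that population with SAP 4.1.7, which requires enough samples to calculate PK parameters.
5. Record the change in SAP Section 5.

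Cost: SAP wording and one derivation from samples already scheduled. Women without Day 60 leave the main summary, which matters with about ten women. The BLQ rule will differ from that of the AUC in 4.5.2 and should be footnoted. AUC/60 does not rescue every gap: with Day 7 missing on 1x600 at 26 days it is off by -25% to +1% (the simple mean by -32% to +6%), so the listing should show which samples each woman had.
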